Study Treatment	Study treatment and follow-up: dose escalation (period 1, 6-weeks) and follow-up (period
Follow-Up	2, 12-weeks)
Efficacy Evaluations	Short-term and longer-term efficacy (urine volume)
	 Among participants with baseline 24-hour urine volume ≥200 mL: incidence of ≥25%
	increase in urine volume
	 Among participants with baseline 24-hour urine volume <200 mL: incidence of a ≥50 mL
	increase in urine volume to a urine volume of at least 100 mL/24-hours
Pharmacokinetic Evaluations	N/A
Safety Evaluations	Short-term and longer-term safety (electrolytes, furosemide levels, BP, symptoms)
	 Incidence of serum potassium <3.2 mEq/L
	 Incidence of serum magnesium <0.8 mg/dL
	 Incidence of serum corrected calcium <7.0 mg/dL
	 Incidence of serum furosemide level >12 microgram/L
	• Incidence of dialysis-associated hypotension requiring hospitalization or treatment in ar
	emergency room and not attributable to overt sepsis, acute myocardial infarction, or
	other cardiovascular event (e.g. aortic dissection)
	• Incidence of severe or very severe patient-reported rash, tinnitus, or hearing change)
	not attributable to causes other than furosemide
	 Incidence of 10-point decrease in Inner Effectiveness of Auditory Rehabilitation (Inner
	EAR) instrument score

Tolerability Evaluations	Short-term and longer-term tolerability (symptoms)							
•	 Incidence of severe or very severe cramping, dizziness/pre-syncope, unusual 							
	tiredness/weakness, chest pain, nausea, vomiting, or diarrhea not attributable to causes other than furosemide							
Statistical And Analytic Plan	At designated study time-points, we will determine the change from baseline for efficacy measures (24-hour urine volume, fractional excretion of urea/ sodium) and safety measures (e.g. potassium, magnesium, hypotension). These measures and absolute change in electrolyte values will be analyzed via one-way repeated measures of analysis of variance to determine the presence of absence of dose-related differences. In addition, we will use mixed effects modeling to test the effect of increased dose and duration with the fixed effect of time (dose), random subject effect, and an unstructured repeated covariance type. We will use generalized estimating equations to assess categorical outcomes (sufficient increase in 24-h urine volume, hypokalemia, hypomagnesemia, hypotension, symptoms, Inner EAR score, patient acceptance). We will also consider binary outcomes as rates (events/time).							

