4 STUDY PROCEDURES

4.1 Overview (Tables 2 and 3)

All study visits will occur at the participant's dialysis clinic at routinely scheduled HD treatments.

- There will be one study visit during the baseline period.
- Dose escalation period (period 1): Blood samples will be collected weekly at mid-week treatment visits (i.e. Wednesday or Thursday during weeks -1, 1, 2, 3, 4, 5 and 6) prior to scheduled dose initiation or dose titration. Urine samples will be collected twice during the dose escalation period at mid-week treatment visits (i.e. Wednesday or Thursday during weeks -1 and 5). Study drug visits will be conducted every two weeks at the first weekly treatment (i.e. Monday or Tuesday during weeks 0, 2, 4, and 6). This structure was selected so that blood results will be collected and analyzed the week prior to study drug dose titration. As such, test results will be available prior to potential dose titration. Adherence and symptom assessment visits will be conducted weekly at the first treatment of each week (i.e. Monday or Tuesday during weeks 1, 2, 3, 4, 5 and 6). Hearing

assessments will be conducted every two weeks at the first weekly treatment (i.e. Monday or Tuesday during weeks 2, 4, and 6).

- Follow-up period (period 2): Blood samples will be collected at mid-week treatment visits every 4 weeks (i.e. Wednesday or Thursday during weeks 9, 13 and 17). Study drug visits will be conducted at the first treatment of each of the subsequent weeks (i.e. Monday or Tuesday during weeks 10 and 14). As in the dose escalation period, this structure was selected so that blood results will be available prior to additional study drug administration. Study adherence and symptom assessment visits will be conducted every 2 weeks at the first weekly HD treatment in the scheduled week (i.e. Monday or Tuesday during weeks 8, 10, 12, 14, 16, and 18). Hearing assessments will be conducted every four weeks at the first weekly treatment (i.e. Monday or Tuesday during weeks 10, 14, and 18). Urine sample visits will be conducted at the mid-week treatments of the 12th week and final week of the follow-up period (i.e. Wednesday or Thursday during weeks 12 and 18). All remaining study drug will be returned at the first weekly treatment (i.e. Monday or Tuesday) of week 19. A final pill count (adherence assessment) will be performed upon study drug return (week 19).

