- All HD treatments occurring during the 18-week study period will be considered study treatments, and all associated clinical data (BP, pre-HD and post-HD weights and dialysis treatment data such as UF volume, UF rate and dialysate composition) will be collected from the electronic health record (EHR).

Table 2. Study visits by	y type.								
Procedures	Baseline clinical assessment (Prior to study start, weeks -4 to -2)	Baseline electrolyte, urine, symptom, and hearing assessment (week -1)	Study drug visit (weeks 0, 2, 4, 6, 10, 14,)	Follow-up blood sample (weeks 1, 2, 3, 4, 5, 6, 9, 13, 17)	Follow-up urine sample (weeks -1, 5, 12, and 18)	Adherence and symptom assessment (weeks 1, 2, 3, 4, 5, 6, 8, 10, 12, 14, 16, and 18)	Hearing assessment (weeks 2, 4, 6, 10, 14, and 18 weeks)	Clinical data collected at every HD treatment during study period (weeks -4 to 18)	Study drug return (week 19)
Complete medical history	х								
Pregnancy status inquiry	Х								
Serum electrolytes and furosemide level		х		х					
24-hour urine		Х			Х				
Symptom assessment		Х				Х			
Hearing assessment		Х					х		
Study drug administration			Х						
Patient acceptance assessment									
Drop-out rates	Х							х	
Pill counts						Х			Х
End of trial study drug return									Х
BP monitoring	Х							х	
Weight monitoring	Х							х	
UF volume/rate	Х							Х	
Extra HD treatments	Х							х	
Hospitalizations	Х							х	

Table 2. Stud	Table 2. Study visits by week.																					
Week(s)	-4 to -2	-1	0	1	2	3	4	5	6	7	8	9	10	11	12	13	14	15	16	17	18	19
Procedures																						
Complete	Х																					

medical history																						
Pregnancy status inquiry	Х																					
Serum electrolytes and furosemide level		x		x	x	x	x	x	х			x				x				x		
24-hour urine		Х						Х							Х						Х	
Symptom assessment		х		х	х	х	х	х	х		х		х		х		х		х		х	
Hearing assessment		х			х		х		х				х				х				х	
Study drug administration			х		х		х		х				х				х					
Patient acceptance assessment				х	х	х	х	х	х		х		х		х		х		х		х	
Drop-out rates	Х	Х	Х	Х	Х	Х	Х	Х	Х	Х	Х	Х	Х	Х	Х	Х	Х	Х	Х	Х	Х	
Pill counts				Х	Х	Х	Х	Х	Х		Х		Х		Х		Х		Х		Х	Х
Study drug return																						Х
BP monitoring	х	x	x	х	х	х	х	х	х	х	х	х	х	х	х	х	х	х	х	х	х	
Weight monitoring	Х	х	х	х	х	х	х	х	Х	Х	х	х	х	х	х	Х	х	х	х	х	х	
UF volume/ rate	Х	Х	Х	Х	Х	Х	Х	Х	Х	Х	Х	Х	Х	Х	Х	Х	Х	Х	Х	Х	Х	
Extra HD treatments	Х	х	х	х	х	х	х	х	х	х	х	х	х	х	х	х	х	х	х	х	х	
Hospitalizations	Х	Х	Х	Х	Х	Х	Х	Х	Х	Х	Х	Х	Х	Х	Х	Х	Х	Х	Х	Х	Х	

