4.4 Follow- up procedures (by visit types)

All study visits will occur at the time of routinely scheduled HD treatments at the patient's usual outpatient dialysis clinic. *Section 5* describes the measurements and assessments in detail.

Blood samples (weeks 1, 2, 3, 4, 5, 6, 10, 14, and 18): Blood will be obtained for the measurement of serum sodium, potassium, chloride, urea, creatinine, magnesium, calcium, albumin, and furosemide level. An additional 2.5 mL blood sample will be drawn, frozen, and stored in UNC Kidney Center -80° freezers for future testing as needed.

Urine samples (weeks -1, 5, 12, and 18): 24-hour urine collections will be obtained for the measurement of urine volume, sodium, urea, creatinine, and furosemide level. An aliquot of urine will be taken from the sample after the before-listed measurements are performed and be frozen and stored in UNC Kidney Center -80° freezers for future testing as needed.

Adherence assessments (weeks 1, 2, 3, 4, 5, 6, 8, 10, 12, 14, 16, and 18): Study staff will complete pill counts.

Acceptance assessments (weeks 1, 2, 3, 4, 5, 6, 8, 10, 12, 14, 16, and 18): Study staff will ask the participant the acceptance question.

Symptom assessments (weeks 1, 2, 3, 4, 5, 6, 8, 10, 12, 14, 16, and 18): Study staff will administer surveys evaluating patient-reported cramping, dizziness/pre-syncope, unusual tiredness/weakness, chest pain, rash, nausea, vomiting, diarrhea, tinnitus, hearing change, and numbness/tingling.

Hearing assessments (weeks 2, 4, 6, 10, 14, and 18): Study staff will administer the Inner EAR instrument.

Clinical data (weeks -4 to 18): HD treatment-level data (BPs, weights, dialysis prescription) will be obtained from the EHR.

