6.3.4 Primary analyses (each assessed separately)

At designated study time-points, we will determine the [data type; see **Section 6.1** for definitions]:

- change from baseline for the short and longer-term efficacy measure [binary] (24-hour urine volume);
- value of short and longer-term safety electrolyte measures [binary] (serum potassium, magnesium, corrected calcium);

- value of serum furosemide levels [binary] (short and longer-term safety furosemide level measure);
- incidence of dialysis-associated hypotension [binary] (short and longer-term safety blood pressure);
- incidence of severe or very severe patient-reported allergic or toxicity-related symptoms [binary] (short and longer-term safety symptom measures);
- change from baseline of Inner EAR instrument score [binary] (short and longer-term safety symptom measure);
- incidence of severe or very severe patient reported symptoms [binary] (short and longer-term tolerability symptom measures);
- incidence of patient-reported acceptance of furosemide [binary] (short and longer-term acceptability measure);
- incidence of adherence by pill counts [binary] (short and longer-term adherence measure).

Change measures and value measures (e.g. 24-hour urine volume, serum electrolytes, serum furosemide level) will be analyzed via one-way repeated measures of analysis of variance to determine the presence of absence of dose-related differences. In addition, we will use mixed effects modeling to test the effect of increased dose and duration with the fixed effect of time (dose), random subject effect, and an unstructured repeated covariance type. We will use generalized estimating equations to assess categorical outcomes (e.g. sufficient increase in 24-h urine volume, hypokalemia, hypomagnesemia, hypotension, symptoms, Inner EAR score, patient acceptance). We will also consider binary outcomes as rates (events/time).

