Analogous to the primary analyses, percentage change measures, change measures, and value measures will be analyzed via one-way repeated measures of analysis of variance to determine the presence of absence of dose-related differences. In addition, we will use mixed effects modeling to test the effect of increased dose and duration with the fixed effect of time (dose), random subject effect, and an unstructured repeated covariance type. We will use generalized estimating equations to assess categorical outcomes. We will also consider binary outcomes as rates (events/time). Distribution of the exploratory parameters will be examined and appropriate transformation will be applied. These analyses are considered hypothesis-generating, and we will examine directionality and strength of relationships but will not assess via p-values.

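### Section 6.3.4 promises a test of dose and duration, but a single time factor in an uncontrolled forced-order titration cannot separate dose from time, and no urine is scheduled at the first two dose steps

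*Combined protocol and SAP*

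**What the plan says.** For measures such as 24-hour urine volume, serum electrolytes and furosemide level, section 6.3.4 says they will be "analyzed via one-way repeated measures of analysis of variance to determine the presence of absence of dose-related differences". It adds that "we will use mixed effects modeling to test the effect of increased dose and duration", through a model with "the fixed effect of time (dose), random subject effect, and an unstructured repeated covariance type". The synopsis has the same plan ("These measures and absolute change in electrolyte values will be analyzed via one-way repeated measures of analysis of variance"). Section 6.3.5 repeats it for the exploratory measures ("Analogous to the primary analyses, percentage change measures, change measures, and value measures will be analyzed via one-way repeated measures") and there sets p-values aside.

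Sections 3.1 and 3.2 describe an open-label, non-randomised study in which everyone takes furosemide. Under sections 1.2 and 3.5.2, participants not on furosemide at entry move through 160, 240 and 320 mg/day in that order, two weeks each. The highest tolerated dose is then held for period 2.

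On urine, section 4.1 says "Urine samples will be collected twice during the dose escalation period at mid-week treatment visits", at weeks -1 and 5. Section 4.4 gives the full schedule as "Urine samples (weeks -1, 5, 12, and 18". Table 2 agrees. Section 4.1 schedules blood weekly during escalation, so it covers every step.

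No section adds a separate dose term, a time-varying dose covariate, or a statement that dose and time are confounded.

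**The concern.** One fixed factor is asked to answer two questions: does more drug do more, and does longer treatment change the effect? In naive participants the dose is set by the calendar, so a difference between visits could come from the dose, from time on drug, or from change unrelated to the drug. With no control, no comparison isolates any of these. Comparing weeks 12 and 18 with week 5 describes change at a held dose, but not whether the drug's duration caused it.

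For urine the schedule adds a second limit. Week 5 falls in the third step (weeks 4 to 6), so nothing is collected during the first two.

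This matters because section 1.3 says that the best dose in HD patients is not known and describes a ceiling above which more drug adds no diuresis. A before-after change reported under a dose heading could be taken as dose-response evidence. In naive completers, the urine data cannot show whether the response was already complete at the first step.

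**Working it through.** **The plan's own figure.** Section 6.4 gives 83% power for a mean urine change of 5 mL/24 h with N = 36, SD of change 10 and two-sided alpha 0.05. A paired t-test has noncentrality (5/10) × √36 = 3 on 35 df, which gives 83.1%. The figure reproduces. It concerns a mean change from baseline and needs no dose contrast.

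**Inputs.** Doses are from sections 1.2 and 3.5.2, urine weeks from 4.1 and 4.4, and blood weeks (-1, 1 to 6, 9, 13, 17) from 4.1. Section 4.4 lists weeks 10, 14 and 18 for the last three blood draws; the dose is held from week 6 in completers, so the rank does not change.

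**Urine, naive completers.** Doses at weeks -1, 5, 12 and 18 are 0, 320, 320 and 320 mg/day. Four visit indicators plus one dose column make 5 columns with rank 4. Dose equals 320 times the sum of the last three visit indicators, so it adds nothing beyond visit.

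**Ceiling.** Let the mean response be K × min(dose, c)/c, where c is the dose at which the response levels off.

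| c (mg/day) | Week -1 | Weeks 5, 12, 18 | At 160 (no urine) | At 240 (no urine) |
|---|---|---|---|---|
| 160 | 0 | K | K | K |
| 240 | 0 | K | 0.67K | K |
| 320 | 0 | K | 0.50K | 0.75K |

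The three cases differ only where no urine is scheduled, whatever the size of K.

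**Blood, naive completers.** Ten visit indicators plus dose make 11 columns with rank 10, whether the week 2 and week 4 samples fall before or after titration.

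**Other dose paths.** Starting from 36 naive completers, replacing one participant gives the following.
- Urine, a prior user assumed at 80 mg/day on entry and 180 mg/day from week 5: rank 5 of 5.
- Urine, a step-back in period 1 (0/240/240/240) or in period 2 (0/320/240/240): rank 5 of 5.
- Blood, one such prior user: rank 11 of 11.

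So the pooled data are not rank deficient. What the added variation buys can be seen from a fit with subject, visit and dose effects at weeks -1 and 5, for naive completers and such prior users. The dose slope is then exactly

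(mean change in naive − mean change in prior users) / (320 − 100),

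where 100 = 180 − 80. This held with 3, 9 or 18 prior users (assumed numbers; the documents give no share). The slope is a comparison of two groups that were not randomised.

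The 180 is illustrative and before rounding to tablet strengths. It takes two successive 50% rises (80 → 120 → 180), as in sections 1.2 and 3.5.2. Section 4.3, week 4, sets the rise against the initial dose, which gives 120 and a divisor of 320 − 40 = 280. Full rank holds either way.

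**Covariance (secondary).** An unstructured matrix has T(T+1)/2 parameters: 10 for 4 urine visits and 55 for 10 blood visits. Adding a random subject variance makes 11 and 56, with only 10 and 55 estimable. If HD session were the repeated unit, 18 × 3 = 54 sessions would need 54 × 55/2 = 1,485 parameters, while a sample covariance from 36 people has rank at most 35.

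**The case against.** The strongest reply is that dose is not tied to week for everyone. Prior loop-diuretic users, step-backs and delayed escalation (section 3.5.3) all vary it, and one such participant restores full rank. That stands: a reader might infer that dose and time are completely aliased across the trial, and the documents support this only for naive completers. But the variation reflects prior treatment, intolerance or interruption, and the stated model has no dose term to use it.

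Second, the reach is limited. The primary urine endpoints are binary and analysed by GEE. Section 6.3.1 puts the emphasis on estimates and intervals, and section 6.3.5 is hypothesis-generating without p-values. This stands for the repeat in 6.3.5. However, the ANOVA sentence in 6.3.4 names urine volume itself, and 6.3.1 sets a 0.05 threshold.

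Third, section 6.4 wants the pilot for the sample size of a later trial, which needs a mean and an SD rather than a dose curve. That is fair. Misuse of a dose label is a risk, not a certainty.

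Fourth, the blood data are better placed. Every step is sampled, the later draws are at a held dose for most participants, and dose becomes estimable if a linear time trend is assumed. That assumption cannot be tested here. For furosemide level the objection largely succeeds: with a terminal half-life of about 2 hours (section 1.2), drift explains little of a rise from a drug-free baseline.

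Fifth, section 3.3 excludes the first 60 days of HD because urine output is likely to fall then. This lessens natural change but does not remove it, since patients at 60 to 180 days are still recruited.

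**Conclusion.** The point holds as a mismatch between the 6.3.4 wording and what the design can identify. For urine in naive completers there is no between-dose contrast: 2 of 4 dose levels are measured, and a ceiling at a lower step cannot be detected. Elsewhere only non-randomised dose contrasts exist, and the specified model does not use them. For blood, the confounding with time matters for electrolytes and little for the rise in furosemide level.

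A reader might also infer that the main efficacy result or its power is undermined. The documents do not support that. Objective 2.1 concerns urine volume at the maximally tolerated dose, and that before-after estimate, the binary responder endpoint and the stated power are unaffected. Nor is any direction or size of bias claimed. The control-group fall in urine volume cited in section 1.3 comes from peritoneal dialysis patients and is not used here.

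The ranks assume the scheduled visit weeks and the stated dose sequence. The prior-user doses and numbers are illustrative. The redundant covariance parameter leaves the visit means unchanged, and the session point applies only if session is the repeated factor. The wording should be corrected before analysis.

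**What to change.** Change the SAP wording and model specification in 6.3.4, 6.3.5 and the synopsis.

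1. Replace the dose-difference aim and the dose-and-duration test with change from baseline at each visit under the titration regimen, with visit as a categorical factor.
2. State that dose and time cannot be separated, and that no urine is scheduled at the first two steps.
3. Show prior-diuretic users separately through the existing 6.3.6 subgroup, because their week -1 value is taken on drug.

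Optional tidying: drop the random subject effect where the residual covariance is unstructured, and use a parsimonious covariance if HD session is the repeated unit.

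Separately, sections 1.2 and 3.5.2 on one side and section 4.3 on the other differ on whether the week 4 rise for prior users is taken from the preceding or the initial dose. The sponsor should reconcile them; no dose is proposed here.

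The cost is text only, with no new visits or samples. The plan gives up its dose-response wording, which the design cannot support.

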6.3.5 Exploratory analyses (each assessed separately)

At designated study time-points, we will determine the [data type; see Section 6.2 for definitions]:

- Absolute change from baseline for the short and longer-term efficacy measure [continuous] (24-hour urine volume);
- percentage change from baseline for the short and longer-term efficacy measure [continuous] (24-hour urine volume);
- absolute change from baseline for the short and longer-term safety electrolyte measures [continuous] (serum potassium, magnesium, corrected calcium);
- percentage change from baseline for the short and longer-term safety electrolyte measures [continuous] (serum potassium, magnesium, corrected calcium);
- occurrence of dialysis-associated hypotension- alternative definition (<80 mmHg) [binary] (short and longerterm safety blood pressure);
- occurrence of dialysis-associated hypotension- alternative definition (<90 mmHg) [binary] (short and longerterm safety blood pressure);
- value of lowest systolic BP during HD [continuous] (short and longer-term safety blood pressure);
- number (percentage) of patients withdrawing from the study [continuous] (short and longer-term acceptability);
- number (percentage) of patients not continuing into period 2 [continuous] (short and longer-term acceptability);
- value of serum furosemide levels [continuous; binary] (short and longer-term acceptability);
- value of urine furosemide levels [continuous; binary] (short and longer-term acceptability);
- absolute change from baseline for 24-hour creatinine clearance [continuous]
- percentage change from baseline for 24-hour creatinine clearance [continuous]
- absolute change from baseline in 24-hour fractional excretion of sodium [continuous]
- percentage change from baseline in 24-hour fractional excretion of sodium [continuous]
- absolute change from baseline in 24-hour fractional excretion of urea [continuous]
- percentage change from baseline in 24-hour fractional excretion of urea [continuous]
- value of pre-HD systolic BP [continuous]
- value of IDWG [continuous]
- value of UF volume [continuous]

- value of UF rate [continuous]
- occurrence of target weight achievement [binary]
- value of post-HD weight and target weight differential [continuous]
- occurrence of extra HD treatments [continuous]
- occurrence of hospitalizations [continuous]

Analogous to the primary analyses, percentage change measures, change measures, and value measures will be analyzed via one-way repeated measures of analysis of variance to determine the presence of absence of dose-related differences. In addition, we will use mixed effects modeling to test the effect of increased dose and duration with the fixed effect of time (dose), random subject effect, and an unstructured repeated covariance type. We will use generalized estimating equations to assess categorical outcomes. We will also consider binary outcomes as rates (events/time). Distribution of the exploratory parameters will be examined and appropriate transformation will be applied. These analyses are considered hypothesis-generating, and we will examine directionality and strength of relationships but will not assess via p-values.

